# Study medication intake

Date/time of first randomized study medication intake is the date/time of first study medication intake recorded at Day 1.

Date/time of last randomized study medication intake is the date/time of last study medication intake recorded in the Study Termination form.

# **6.2** EXTENT OF EXPOSURE

Extent of exposure will be calculated in hours as difference between end date/time of infusion and start date/time of infusion:

Extent of exposure (hours) = end date/time of infusion - start date/time of infusion

# 6.3 EFFICACY VARIABLES

# AUC0-48h on changes in dyspnoea

AUC0-48h on changes in dyspnoea will be calculated using the following formula:

$$AUC_{0-48h} = \sum_{i=3h}^{48h} \frac{(t_i - t_{i-1})(\Delta VAS_i + \Delta VAS_{i-1})}{2}$$

with i = 3, 6, 12, 24, 48 hours.

1.0/30/10/2018 Page 13 of 28

In the above formula,  $t_i$  represents the scheduled timepoints in hours for VAS score measurements (see table below) and  $\Delta VAS_i$  represents the change from pre-dose of the value of the VAS score at the timepoint i. The change from pre-dose at the timepoint i = 0 will be zero.

Time of evaluation (hours)					
T pre- dose	T3h	T6h	T12h	T24h	T48h
$t_0$	$t_1$	t 2	t 3	t 4	t 5
Time point for calculation					

The scheduled timepoint will be used for the calculation of AUC0-48h.

In the calculation of  $AUC_{0-48h}$ , missing values will be replaced as follows:

- single, isolated missing values (different from pre-dose and last value) will be replaced by linear interpolation using the adjacent values;
- if the last value is missing, it will be replaced by the previous value;
- in case of pre-dose value is missing and/or two or more consecutive values are missing and/or three or more values are missing, no replacement will be performed and the entire curve will be considered as missing.

The AUC0-48h will be calculated after the replacement of missing values.

AUC0-48h will be calculated only for patients with VAS score at screening different from 100 or missing.

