
Globally, istaroxime was well tolerated and safe up to 1.5 μg/kg/min in patients suffering from acute HF. Doses above 1.5 μg/kg/min were not completely tolerated due to *Protocol N°: CVT-CV-002*

gastrointestinal disorders and infusion site pain.

In conclusion, in this study the lowest tested dose of $0.5 \mu g/kg/min$ of istaroxime infused for 6 hours produces a significant PWCP improvement over placebo, being the istaroxime safety profile satisfactory even at higher dose, in this setting.

Pharmacokinetic results showed that istaroxime levels increased proportionally in plasma reaching steady state concentration within the 1hour infusion. Estimated half-life for istaroxime was about 10 to 20 minutes at infusion rates higher than 1.66 μ g/kg/min. For rates of infusion lower than 1.66 μ g/kg/min, concentration dropped below the limit of quantification (10 ng/ml) at 5 min after stopping of the infusion.

The systemic exposure to istaroxime resulted to be linearly related to the administered dose [20]. A very high clearance was shown, resulting around 4500 ml/min for a 70 kg body weight man. The concentration of PST 2915, the main metabolite (6β-alcholol) of the parent compound, was also measured, showing that its concentration slowly increased during infusion period, reaching a maximum concentration within 10 min after the stop of the intravenous infusion of istaroxime [20]. The metabolite maximum concentration resulted to be about one half of the corresponding C_{max} of istaroxime. Half-life of PST 2915 resulted to be around 3 to 4.5 hours [20]. PST 2915 resulted to be an active metabolite showing the same stimulatory activity on SERCA2a of istaroxime but about 10 time less inhibitory activity on Na-KATPase and potency in in vivo animal models than istaroxime [20].

For infusion longer than 1 hour, PST 2915 plasma concentrations increase with time, while those of istaroxime remain at steady state, being constant the rate of infusion.

To evaluate the risk of a prolongation of istaroxime intravenous infusion over six hours, pharmacokinetic, efficacy and tolerability clinical studies have to be carried out. The above clinical evidence indicates that istaroxime could be a future treatment option for patients with ADHF and a low cardiac output state.

More detailed clinical information can be found in the Investigator's Drug Brochure [20].

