## Dyspnoea using VAS score

Analysis will be performed only for patients with VAS score at screening different from 100 or missing.

Dyspnoea using VAS score and changes from baseline will be summarized at each timepoint by treatment group by means of descriptive statistics.

Changes in dyspnoea using VAS score will be analyzed using a MMRM with change from baseline in dyspnoea using VAS score at 3, 6, 12, 24, 48 hours as dependent variable, treatment, centre, timepoint, gender, baseline cTnT (normal <URL, abnormal ≥URL), atrial fibrillation (Yes/No) and treatment\*timepoint interaction and baseline and baseline\*timepoint interaction as covariates. An unstructured covariance matrix will be considered and the Kenward-Roger adjustment will be used for the degrees of freedom. Only pre-dose, 3, 6, 12, 24, 48 hours values after infusion start will be considered in the MMRM.

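### The dyspnoea AUC0-48h rule fills a missing 48 h score with the end-of-infusion score and voids the curves of patients last measured before 24 h; the carry-forward can bias the difference in either direction, and one MMRM contrast avoids both

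*SAP*

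**What the plan says.** SAP 6.3 computes the AUC of the change in VAS by the trapezoid rule at the scheduled times, "with i = 3, 6, 12, 24, 48 hours", with the change at time 0 set to zero. Three rules cover gaps:

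- Middle gap: "single, isolated missing values (different from pre-dose and last value) will be replaced by linear interpolation using the adjacent values".
- Missing 48 h value: "if the last value is missing, it will be replaced by the previous value".
- Larger gaps, meaning no pre-dose score, at least two gaps in a row, or at least three in all: "no replacement will be performed and the entire curve will be considered as missing".

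The AUC then goes into an ANCOVA (SAP 7.7.2), analysed on the ITT population with the cohorts combined. SAP 5.1 requires only one post-baseline efficacy evaluation for ITT. SAP 7.1 refers back to section 6.3 for missing data and leaves only other critical gaps to the blind review. SAP 7.9 plans no further analyses.

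The same readings have a second analysis in SAP 7.7.2: "Changes in dyspnoea using VAS score will be analyzed using a MMRM". It uses the changes at 3 to 48 h with an unstructured covariance, and no carry-forward or curve deletion is stated.

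The infusion lasts 24 h (protocol synopsis). On elimination, protocol 1.2 says: "Estimated half-life for istaroxime was about 10 to 20 minutes at infusion rates higher than 1.66" (rate in µg/kg/min). For lower rates it reports concentrations below quantification 5 minutes after stopping. It gives the active metabolite a half-life of about 3 to 4.5 h.

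**The concern.** The infusion is due to stop at 24 h, so the interval from 24 to 48 h is off drug. A patient without a 48 h score is credited with the 24 h score at 48 h. If relief fades once the infusion stops, that credit is too generous. Between 24 and 48 h about 5 to 8 metabolite half-lives pass (24/4.5 to 24/3), so fading is plausible.

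The deletion rule affects other patients. Someone measured at 3, 6 and 12 h and then lost has two consecutive gaps and no AUC, although the patient is in the ITT set named for this endpoint. Such losses need not be random. Protocol 5.7 ends the infusion if a rescue inotrope is needed, and protocol 5.2 treats an emergency code break as a drop-out. Where such an event also ends VAS collection before 24 h, clinical course decides who is left out.

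At stake is the size of the treatment difference on one secondary endpoint, and which patients it describes.

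**Working it through.** The plan states no effect, SD, power or missing rate for this AUC, so there is no figure to reproduce. The check derives what the rules do.

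**Weights.** Each time receives half of each adjoining interval (SAP 6.3 formula):

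- 0 h: 1.5 (change fixed at 0)
- 3 h: (3 + 3)/2 = 3
- 6 h: (3 + 6)/2 = 4.5
- 12 h: (6 + 12)/2 = 9
- 24 h: (12 + 24)/2 = 18
- 48 h: 24/2 = 12

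The total is 48. With 48 h carried forward, the weight on the 24 h score rises from 18/48 (37.5%) to 30/48 (62.5%).

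**What the rules do by last observed score**

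| Last VAS | Result |
|---|---|
| pre-dose, 3, 6 or 12 h | curve void |
| 24 h | 24 h score carried to 48 h |
| 48 h | no carry-forward |

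If 24 h is missing as well, the curve is void, so the value carried forward is always an observed 24 h score.

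**Bias from the carry-forward.** One patient's error is 12 × (change at 24 h − change at 48 h). Let T and P be the mean changes on istaroxime and placebo, and mT and mP the shares missing only 48 h, with missingness unrelated to outcome. Then

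bias = 12 × [mT(T24 − T48) − mP(P24 − P48)].

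With mT = mP = m and effect d = T − P, this is 12 × m × (d24 − d48).

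**Equal missingness.** Assume an effect of 10 mm at 3 to 24 h. The true AUC difference is 10 × (3 + 4.5 + 9 + 18) = 345 mm·h plus 12 × d48.

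| Effect kept at 48 h | True difference | Bias at 10% missing | Bias at 20% missing |
|---|---|---|---|
| none | 345 | +12 (+3.5%) | +24 (+7.0%) |
| half | 405 | +6 (+1.5%) | +12 (+3.0%) |
| all | 465 | 0 | 0 |
| 25% larger | 495 | −3 (−0.6%) | −6 (−1.2%) |

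A slower onset changes little. With 5 mm at 3 h, 10 mm at 6 to 24 h and none at 48 h, the true difference is 15 + 315 = 330. At 20% missing it becomes 354 (+7.3%).

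**Unequal missingness.** Assume both arms keep improving from 24 to 48 h, by 5 mm on drug and 10 mm on placebo, so the effect wanes by 5 mm.

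- 10% missing in each arm: 12 × [0.10 × (−5) − 0.10 × (−10)] = +6 mm·h.
- 20% on drug, 5% on placebo: 12 × [0.20 × (−5) − 0.05 × (−10)] = −6 mm·h.

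If both arms improve by 5 mm (no waning), 20% against 5% gives 12 × [0.20 × (−5) − 0.05 × (−5)] = −9 mm·h.

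**Voided curves.** If 5%, 10% or 20% of a group of 40 have their last score before 24 h, 38, 36 or 32 have an AUC.

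**The case against.** A reader might infer that the rule inflates the benefit of istaroxime. The documents do not support that. The direction depends on whether relief wanes and on missingness by arm, and neither document gives a dyspnoea effect at 24 or 48 h or a VAS missing rate. The half-lives make waning plausible but do not show it. The 10 to 20 minute figure comes from rates above those used here, the metabolite accumulates during longer infusions, and plasma half-life is not duration of symptom relief.

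A reader might also infer that the problem would be hidden. It would not be. SAP 7.7.2 reports VAS and its change by timepoint and arm, SAP 7.4 includes n in those summaries, and the AUC analysis reports the number of patients in the model. Nor are early leavers lost from dyspnoea altogether, because the VAS MMRM keeps their observed scores. Stopping the infusion does not by itself stop VAS assessment.

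The exposure is also smaller than half of the window: the replaced value carries 12 of 48 h, because the observed 24 h score already carries the other half of the last interval. Many 48 h scores may well be present, since the SAP counts hospital stay from 4 days and protocol 15 aims to keep drop-out within 20%. Finally, the protocol itself specifies the ANCOVA, and this is one secondary endpoint of a phase II trial.

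All of this stands, and it limits the size. It does not remove the carry-forward or the exclusion, and no AUC analysis without them is planned. A bias of unpredictable sign is itself a reason not to carry forward.

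**Conclusion.** The concern holds in conditional form. It is certain from the text that a missing 48 h score is replaced by the end-of-infusion score, and that ITT patients last measured at 3, 6 or 12 h have no AUC. The carry-forward can bias the AUC difference. Under equal missingness unrelated to outcome and a roughly constant effect up to 24 h, it overstates a waning effect by about 7% or less at 20% missing, and by nothing if there is no waning. Under unequal missingness the sign can reverse, and bias can arise without waning. The effect of voiding early curves cannot be sized from the documents. This is a cheap improvement to a secondary endpoint and does not threaten the trial's main conclusion.

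**What to change.** 1. In SAP 6.3, delete the last-value replacement.
2. Estimate the AUC0-48h difference for each dose against placebo as a linear contrast of the treatment-by-timepoint means from the VAS MMRM in SAP 7.7.2 and 9.0, with weights 3, 4.5, 9, 18 and 12 h at 3, 6, 12, 24 and 48 h. The coefficient on the treatment main effect is their sum, 46.5. The model already has the interaction, the unstructured covariance and the covariates of the AUC ANCOVA.
3. Keep the protocol's per-patient ANCOVA beside it, on curves without carry-forward.
4. Report AUC0-24h, with weights 3, 4.5, 9 and (24 − 12)/2 = 6 h at 3, 6, 12 and 24 h, and missing VAS counts by arm and timepoint.
5. List the departure from the protocol's ANCOVA in SAP 1.1.

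The cost is SAP wording and one ESTIMATE statement per dose. The contrast relies on the missing-at-random assumption already made for the VAS MMRM. It also implicitly extrapolates scores after death, so deaths before 48 h should be reported by arm. The retained ANCOVA will rest on fewer patients.

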#### Length of hospitalization (days)

Length of hospitalization will be calculated using the following formula:

Length of hospitalization = 4 + Number of days of hospitalization after day 4

If the variable "Number of days of hospitalization after day 4" is missing, the length of hospitalisation will be 4 and the number of days of hospitalization after day 4 considered in the analysis will be zero.

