#### 5.0 ANALYSIS SETS

#### INTENT-TO-TREAT POPULATION (ITT) 5.1

All randomized patients who will receive at least one administration of the study medication and with at least one available evaluation of efficacy after the baseline will be included in the ITT population.

The ITT population is the primary population for the efficacy analysis.

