# 7.0 STATISTICAL METHODOLOGY

## 7.1 HANDLING OF MISSING DATA

The number of patients with missing data will be presented under the "Missing" category, if present. Missing values will be included in the denominator count when computing percentages.

When continuous data are being summarised, only the non-missing values will be evaluated for computing summary statistics.

Missing or incomplete data will be treated as described in sections 6.1, 6.3 and 6.4.

There will be no imputation of missing echocardiographic data.

Other critical missing data will be discussed prior to treatment unblinding, if any. Decisions will be taken during the blind review of the data and will be fully documented in the Data Review Report.

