# 7.4 GENERAL METHODOLOGY

Descriptive statistics will be provided for all variables in the summary tables by treatment group according to the type of variable summarized.

Quantitative variables will be summarised by using n, mean, standard deviation (SD), 95% confidence interval (CI) of the mean, median and range (minimum and maximum). Categorical variables will be summarised by using frequency distributions and percentages.

Hypothesis testing will be carried out at the alpha = 0.05 level (two-sided) when comparing treatments. For all inferential analyses, p-value will be rounded to three decimal places. Statistical significance will be declared if the rounded p-value will be less than or equal to 0.05.

Statistical analyses will be carried-out pooling together the patients treated with placebo in the two groups with the exception of the echocardiographic parameters that will be analysed separately for each cohort.

All data collected in the CRF will be presented in the listings.

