# 7.7.2 Secondary efficacy endpoints

For echocardiographic parameters, analysis will be performed separately for each cohort on ITT population.

For all other endpoints, analysis will be performed using the combined cohorts on ITT population.

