# Length of hospitalization

Length of hospitalization and the number days of hospitalization after day 4 will be summarized by treatment group using descriptive statistics.

1.0/ 30/10/2018 Page 21 of 28

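### SAP 6.3 turns any blank later-days field into a 4-day stay, so an unknown longer stay can be summarised as an observed short one

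*SAP*

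**What the plan says.** SAP 6.3 derives the endpoint from one collected field: "Length of hospitalization = 4 + Number of days of hospitalization after day 4". If that field is left blank, "the length of hospitalisation will be 4 and the number of days of hospitalization after day 4 considered in the analysis will be zero". The missing field is the only trigger. Nothing is said about discharge, death, withdrawal or a stay of unknown length.

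SAP 7.1 does not override this. It points back to the rule: "Missing or incomplete data will be treated as described in sections 6.1, 6.3 and 6.4". Its blind-review clause is reserved for other critical missing data, so it does not reach this field.

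SAP 7.7.2 places the endpoint among the secondary efficacy endpoints outside echocardiography: "For all other endpoints, analysis will be performed using the combined cohorts on ITT population". Under its own heading, length of hospitalization "will be summarized by treatment group using descriptive statistics". No test, count of substituted values or sensitivity summary is planned. SAP 7.4 adds: "Statistical analyses will be carried-out pooling together the patients treated with placebo in the two groups", with an exception only for echocardiography. To be in the ITT population (SAP 5.1) a patient must have received study medication and be among those "with at least one available evaluation of efficacy after the baseline will be included in the ITT population".

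Two other places bear on the point. For the dyspnoea AUC, also in SAP 6.3, when the pre-dose value or too many later values are missing, "no replacement will be performed and the entire curve will be considered as missing". Protocol 13.2 and 13.3 plan automated checks for missing data, queries to sites, and lock once the data are clean.

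**The concern.** The rule treats two different situations alike. A patient known to have left hospital by Day 4 has no later days, so zero is a fact. A patient whose later days were never recorded has an unknown number, and zero is then the most favourable value possible. Both appear in the table as a 4-day stay and both count in n.

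Such a patient can reach the table. The ITT definition can be met as early as the 3-hour dyspnoea assessment, so someone who withdraws or is lost after that, with the field blank, is included. The descriptive table is the only planned output for this endpoint, so its mean and n are the result. Listings would show the raw blank, but the general flag for derived variables does not separate a substituted 4 from an observed one, and a listing does not correct the summary.

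A smaller, separate problem lies in the formula. The 4 is fixed, so a stay ending before Day 4 cannot be represented even when it is known. Protocol sections 8 and 9 allow for assessment at Day 4 or at discharge, which leaves earlier discharge open.

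**Working it through.** **Inputs.** The formula and missing-value rule come from SAP 6.3. Arm size comes from SAP 4.0 and 7.4: 40 per istaroxime dose, and 20 + 20 = 40 pooled placebo, taking planned numbers as the ITT size. The documents give neither the number of blanks nor any length of stay. True stays of 8, 10 and 14 days are therefore assumptions, as is the example in step 6.

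**1. The plan's own figure.** Blank field: 4 + 0 = 4 days. The minimum of 4 + d over d ≥ 0 is also 4. The plan's value is reproduced and equals the formula's floor.

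**2. What the rule does with different patients.**
- Discharged on Day 4, later days recorded as 0: true 4, tabulated 4.
- Discharged on Day 4, field blank: true 4, tabulated 4.
- In hospital for 14 days, field blank: true 14, tabulated 4.
- Stay ended on Day 2, field blank or 0: true 2, tabulated 4.

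The summary cannot tell these apart.

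**3. Shift in one arm's mean.** With k patients whose unknown stay is coded as 4, and true mean stay L among them, the mean falls by k × (L − 4) / 40.
- k = 1: 4/40 = 0.10, 6/40 = 0.15 and 10/40 = 0.25 days for L = 8, 10 and 14.
- k = 2: 0.20, 0.30 and 0.50 days.
- k = 3: 0.30, 0.45 and 0.75 days.

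**4. Difference between arms.** With the same L in both arms, the spurious difference is (k₁ − k₂) × (L − 4) / 40. It is zero when k₁ = k₂. An excess of 1, 2 or 3 such patients in one arm gives 0.10–0.25, 0.20–0.50 or 0.30–0.75 days.

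**5. Stays ending before Day 4.** These are overstated by 4 − 3 = 1 day or 4 − 2 = 2 days. Per patient, the arm mean rises by 1/40 = 0.025 or 2/40 = 0.05 days, opposite in direction to step 3.

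**6. What happens if all blanks are simply set to missing.** Suppose 10 of 40 patients have a blank, all truly discharged on Day 4, and the other 30 average 10 days. The SAP rule gives (10 × 4 + 30 × 10) / 40 = 340/40 = 8.5 days, which is correct. Dropping the blanks gives 10.0 days, an error of +1.5 days. A crude remedy can therefore do more harm than the rule.

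**The case against.** The strongest reply is that the CRF, which is not among the documents, may intend a blank to mean no days after Day 4. The SAP rule would then be a coding convention and no stay would be invented. This stands for every patient to whom it applies. It does not remove the point, because the SAP does not say that a blank has this meaning.

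Second, the protocol already plans to find missing data, query sites and lock only clean data. This also stands, and it should reduce the number of unexplained blanks. It does not say what happens to one that remains, and the SAP rule then applies.

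Third, the contrast with the dyspnoea AUC can be pressed too far. The same section carries the previous value forward when the last one is missing, and a curve is a different structure from one count. The AUC shows only that the SAP knows how to leave a value missing when too little is known.

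A reader might go further and infer that in-hospital deaths will be reported as 4-day stays, and might scale the bias from the registry mortality in the protocol's introduction. The documents do not support this. Nothing says a death leaves the field blank: for a death on Day 10 the days after Day 4 can be counted, and for a death on Day 4 zero is correct. The registry figure also describes a broader population than this trial's eligibility criteria admit.

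**Conclusion.** The point holds as a low-severity gap. SAP 6.3 states a rule that gives the wrong value for any blank hiding a longer stay, and the fixed 4 gives the wrong value for any stay ending before Day 4. Neither document confines the rule to patients discharged by Day 4.

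The size is 0.10 to 0.25 days on an arm mean of 40 per affected patient, if true stays are 8 to 14 days. It is nil if every blank is a Day 4 discharge. The number of affected patients is unknown.

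Two stronger conclusions are not supported. The SAP does not contradict itself, since SAP 7.1 sends the reader to the SAP 6.3 rule. Nor is there evidence that the rule favours istaroxime, since a between-arm difference needs unequal numbers of such blanks or unequal true stays. The endpoint is untested, so the primary analysis and the error rate are unaffected.

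**What to change.** Amend SAP 6.3, in this order:

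1. State what a blank means. Set later days to 0 only where discharge by Day 4 is documented, or where the CRF defines a blank that way.
2. Resolve other blanks before lock through the query process already planned in protocol 13.2 and 13.3. Check fatal adverse event outcomes (SAP 6.4) and reasons for discontinuation (SAP 7.5) first.
3. Leave only the unresolved ones missing and report their number by arm.
4. Show the summary both with and without the 4-day substitution, because dropping true Day 4 discharges would push the mean up.
5. Where a date of discharge or death is collected, use it for stays ending before Day 4. Report any in-hospital deaths in a separate row.

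The cost is a short SAP amendment, one changed derivation, two extra rows (missing, died in hospital) and a second version of one descriptive summary. A few queries are likely. If the CRF does not define a blank, they could extend to every Day 4 discharge, and checking existing records first would shorten the list. The n behind the mean may be slightly smaller.
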